16.1.4.3. Tipping point analysis

All ITT subjects are included in tipping point analysis.

Sensitivity to departures from the MAR assumption will also be investigated using a tipping point analysis. In this analysis, departures from MAR in the SEP-4199 (200 mg and 400 mg) group will be assessed assuming that subjects who discontinue the study have, on average, efficacy outcomes after discontinuation that are worse by some amount δ (ie, a percentage of the LS mean treatment difference) compared to other similar subjects with observed data at the same time point (ie, compared to a value which would have been assumed under a MAR model).

A series of analyses will be performed with increasing values of δ until the analysis conclusion of a statistically significant treatment effect no longer holds. The value of δ that overturns the primary results will represent a tipping point. An interpretation of clinical plausibility of the assumption underlying the tipping point will be provided. After one treatment group comparison reaches the tipping point, the analyses will continue for the other treatment group comparison until it reaches the tipping point.

Change from baseline in MADRS total score will be analyzed based on data observed while the subject remains on study as well as data imputed using multiple imputation methodology for the time points at which no value is observed. Intermittent (non-monotone) missing data will be imputed first based on the MAR assumption and a multivariate joint Gaussian imputation model using the MCMC method within each treatment group, as described above for the pattern-mixture model with placebo-based multiple imputation.

Document:

Author:

Version Number:

V2.0

Version Date:

21MAY2020

Template No: CS_TP_BS016 Revision 4
Effective Date: 01Apr2016

Reference: CS_WI_BS005

The remaining monotone missing data will be imputed using sequential regression multiple imputation, where a separate regression model is estimated for imputation of each variable (ie, MADRS total score at each time point). Each regression model will include explanatory variables for treatment and all previous (Baseline, Week 1, Week 2, and Week 4) values of MADRS total score.

After the MAR-based imputations have been generated for MADRS total score at each time point, a value of δ will be added to all imputed change from baseline values in the SEP-4199 (200 mg or 400 mg) group. This approach assumes that the marginal mean of unobserved subject measurements is worse by δ at each time point after discontinuation compared to the marginal mean of subjects with observed data at the same time point.

No rounding restriction will be applied to imputed continuous values. The imputed MADRS total scores must be within the range of 0 to 60.

A total of 1000 imputed datasets will be generated. The random seed number is 12345 for the partial imputation step and 56789 for the sequential regression multiple imputation step.

Each of the 1000 imputed and δ -adjusted datasets will be analyzed using the same MMRM model as the primary efficacy analysis. Results from the analysis of each imputed dataset, ie, the LS mean treatment difference and its standard error, will be combined using Rubin's imputation rules (using the SAS MIANALYZE procedure) to produce a pooled LS mean estimate of treatment difference, its standard error and 95% CI, and a pooled p-value for the test of null hypothesis of no treatment effect.

Analyses will be conducted with different values of δ at each visit, which represents a percentage of the LS mean treatment difference at that visit, starting at 5% with 5% increments, until either the tipping point is identified or the 100% penalty is applied. The actual δ for each percent increment will be presented in the table.

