6.6. STATISTICAL TESTS

All statistical inference will be performed with 2-sided tests at the significance level of 0.05 and 2-sided 95% confidence intervals (CIs), unless otherwise specified in the description of the analyses.

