7.4. MULTIPLE COMPARISONS/ MULTIPLICITY

The truncated Hochberg gatekeeping (with the truncation parameter $\gamma = 0.9$) procedure constructed using the general mixture method will be used to control the global Family-Wise Error Rate (FWER) at 5% for the primary (E1) and secondary endpoint (E2) ([Dmitrenko 2016](#)). Using this method, a hypothesis is testable in a latter family only if the hypothesis in the former family associated with the same dose level is rejected.

The hypotheses associated with the primary and the secondary endpoints will be grouped into 2 hierarchical families as seen in Figure 2 below (See [Sections 16.1.3](#) and [16.2.3](#) for the primary hypotheses [H1, H2] and secondary hypotheses [H3, H4]).

- Family F1: SEP-4199 200 mg/day versus placebo (H_1), and SEP-4199 400 mg/day versus placebo (H_2), based on change from baseline in MADRS total score at Week 6 (E1)
- Family F2: SEP-4199 200 mg/day versus placebo (H_3), and SEP-4199 400 mg/day versus placebo (H_4) based on change from baseline in CGI-BP-S depression score at Week 6 (E2)

Document:

Author:

Version Number:

V2.0

[figure not shown]
Version Date:

21MAY2020

Template No: CS_TP_BS016 Revision 4
Effective Date: 01Apr2016

Reference: CS_WI_BS005

Figure 2: Hierarchy of Testing for Primary and Secondary Endpoints

The mixture-based gatekeeping procedure will be performed in 2 steps:

- Step 1: The SEP-4199 vs placebo comparisons for E1 (hypotheses H1 and H2) will be performed using a truncated Hochberg ($\gamma = 0.9$) test.
- Step 2: The SEP-4199 vs placebo comparisons for E2 (hypotheses H3 and H4) will be performed using a regular Hochberg test only when the corresponding comparisons from Step 1 are rejected. For example, H4 is tested only if H2 is rejected.

The primary efficacy analysis will be repeated for the PP population to provide additional information on the robustness of the primary efficacy results. The Hochberg procedure will not be used for the PP population or for the analysis of Japan and pooled cohorts EU/US + Japan.

Adjusted p-values will be calculated using the SAS-based TreeGate macro and available in following website: http://multxpert.com/wiki/TreeGate_macro.

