robustness of the conclusions, as indicated in [Section 16.2.4](#).

D. Population level summary of the variable: Difference in means of change from baseline in MADRS total score at Week 6 comparing each SEP-4199 treatment group to placebo

The efficacy of SEP-4199 in terms of the MADRS total score will be evaluated using the following two null hypotheses:

H1: There is no difference in mean change from baseline at Week 6 on the MADRS total score in the SEP-4199 200 mg treatment arm compared to Placebo.

H2: There is no difference in mean change from baseline at Week 6 on the MADRS total score in the SEP-4199 400 mg treatment arm compared to Placebo.

The alternative hypothesis for each of the null hypotheses is that there is a difference. If at least 1 of the primary treatment group comparisons demonstrate a significant result, the study will be considered positive.

The primary efficacy endpoint will be analyzed for the ITT population using an MMRM analysis, with change from baseline in the MADRS total score as the response variable and with factors for treatment group, week, region, baseline MADRS total score, and the treatment-by-week interaction. This analysis method makes an MAR assumption to the missing primary efficacy endpoints. The Kenward Roger approximation will be used to estimate denominator degrees of freedom. An unstructured covariance matrix will be used for the within-subject correlation. A robust sandwich estimator for the standard error of the fixed effects ([Diggle 2002](#)) along with a spatial exponential or a spatial power covariance structures will be assumed sequentially in case the model fails to convergence. The first covariance structure to yield convergence will be used in the analysis.

The Least Square (LS) mean treatment differences (each SEP-4199 group minus placebo) of change from baseline at Week 6, their 2-sided 95% CIs, and the associated p-values will be calculated based on the MMRM. The LS mean of change from baseline over time will be plotted. Adjusted p-values will be calculated using a truncated Hochberg procedure with gamma parameter=0.9 (See [Section 7.4](#)).

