Step 5: Fit the primary MMRM model for each penalty and imputation to obtain the estimates at each postbaseline visit.

Suppose the primary MMRM model adopted the unstructured covariance model:

```
ODS OUTPUT DIFFS=CHGDIFF_TIPPING LSMEANS=CHGLSMN_TIPPING;
PROC MIXED DATA=ANALYSIS_PENALTY;
  BY DELTA _IMPUTATION_;
  CLASS SUBJID REGION TRTP WEEK;
  MODEL TOTCFB = TOTBL REGION TRTP WEEK TRTP*WEEK / DDFM=KR;
  REPEATED WEEK / SUB=SUBJID TYPE=UN;
  LSMEANS TRTP*WEEK / PDIFF CL;
RUN;
```

Step 6: Use proc MIANALYZE similar to above to combine the estimates from each imputation for each delta using Rubin's rules. See example for LS Means below.

```
ODS OUTPUT PARAMETERESTIMATES=LSMEST_TIPPING_MIAN;
PROC MIANALYZE DATA = CHGLSMN_TIPPING;
  BY DELTA TRTP WEEK;
  MODELEFFECTS ESTIMATE;
  STDERR STDERR;
RUN;
```

This analysis is repeated for a range of deltas, starting at 0% of the treatment difference at each postbaseline visit, and increasing in increments of 5% until either the tipping point (where the statistical significance of the treatment effect is lost) is identified or the 100% penalty is applied. Tipping point could be reached at different deltas for each SEP-4199 treatment group. Once the tipping point %delta is identified, smaller %delta increments (eg 1%) may be selected for further analysis.

Document:

Author:

Version Number:
Version Date:

V2.0

21MAY2020

Template No: CS_TP_BS016 Revision 4
Effective Date: 01Apr2016

Reference: CS_WI_BS005

MCP-MOD ANALYSIS

The primary efficacy endpoint, change from baseline in MADRS score at Week 6, will also be analyzed using the gMCP-Mod approach for the ITT population. The analysis will be done in two steps.

Step 1: MCP step

The MCP step consists of specifying a set of candidate models for the dose response relationship. First, the following four candidate model families will be selected to describe the potential dose-response curve $f(d, \theta)$.

- Linear model: $f(d, \theta) = E_0 + \delta d$

For the linear model, E_0 is the drug effect at $d \approx 0$ and δ is the slope associated with d . There is no parameter to be estimated for the linear model.

- Quadratic model: $f(d, \theta) = d + \delta d^2$

The quadratic model is intended to capture a possible non-monotonic dose-response relationship. For the quadratic model, there is one parameter δ to be estimated.

- E_{\max} model: $f(d, \theta) = E_0 + E_{\max} d / (ED_{50} + d)$

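### The tipping-point criterion is not tied to the truncated-Hochberg decision, so applying the default 0.05 to raw p-values would overstate robustness, mostly modestly

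*SAP*

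**What the plan says.** - **Primary decision.** SAP 16.1.3: "Adjusted p-values will be calculated using a truncated Hochberg procedure with gamma parameter=0.9". SAP 7.4 sets up the two-dose MADRS family and assigns the adjusted p-values to the TreeGate macro.
- **Tipping-point stop.** SAP 16.1.4.3 increases the penalty "until the analysis conclusion of a statistically significant treatment effect no longer holds". It then says that the delta "that overturns the primary results will represent a tipping point". When one dose has tipped, the search carries on for the other dose until that one tips too.
- **Appendix 3.** The series ends when "the tipping point (where the statistical significance of the treatment effect is lost) is identified" or at the 100% cap. Step 4 applies one common percentage to both doses. Steps 5 and 6 fit the MMRM and pool with MIANALYZE; no multiplicity step follows.
- **Output.** A pooled difference, its standard error, a 95% CI and "a pooled p-value for the test of null hypothesis of no treatment effect".
- **Default level.** SAP 6.6: "All statistical inference will be performed with 2-sided tests at the significance level of 0.05", subject to anything different stated in the description of an analysis.
- **Exemptions.** SAP 7.4: "The Hochberg procedure will not be used for the PP population or for the analysis of Japan and pooled cohorts". The US/Europe tipping-point analysis is not among the exemptions.

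**The concern.** The two parts of the plan use different yardsticks. The claim being stress-tested is a truncated-Hochberg rejection, in which one dose's threshold depends on the other dose's p-value. The stress test is written as two separate searches on raw p-values. A programmer following Appendix 3 has no level to use except 0.05 and no step that would produce an adjusted p-value.

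Two situations go wrong on that reading. A dose that wins alone needs p at or below 0.025, so a penalised p between 0.025 and 0.05 is already a lost claim but is still counted as significant. And where both doses won at first, once the weaker has tipped the stronger must meet 0.025, which the separate search ignores.

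At stake is the reported tipping delta. SAP 16.1.4.3 asks for a clinical-plausibility judgement at that delta, so an inflated value carries into that judgement. Near the 100% cap, a claim that fails could be reported as never tipping.

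**Working it through.** **Inputs.** From the SAP: gamma 0.9 and two hypotheses (7.4, 16.1.3); 93 per arm and effect size 0.44 = 3.85/8.745 (3.4); Scenario 2 effects 0.22 and 0.44 (Appendix 4, Table 6); 5% steps capped at 100% (16.1.4.3). Not in the documents: the share d of an active arm missing at Week 6. Assumed 10% to 30%, equal in both active arms.

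**Critical levels, two tests, 2-sided.**
- Larger p: (0.9 + 0.1/2) x 0.05 = 0.0475, z = 1.982.
- Smaller p: (0.9/2 + 0.1/2) x 0.05 = 0.025, z = 2.241.
- Default: 0.05, z = 1.960.

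**Reproducing the plan's power.** One million draws of two Z statistics sharing a placebo arm, each with mean effect size x sqrt(93/2), judged at these levels (at least one / both):
- Scenario 1: 90.5% / 75.2%; Table 8 gives 0.9027 / 0.7517.
- Scenario 2: 79.2% / 30.2%; Table 9 gives 0.7885 / 0.2996.

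The levels are therefore those behind the stated power.

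**Tipping formula.** Adding a fraction k of the treatment difference to the missing share d shrinks Z to about Z0(1 - kd), with the standard error held fixed. So k = (1 - zc/Z0)/d. The overstatement ratio, 0.05 against the correct level, is (Z0 - 1.960)/(Z0 - zc), which does not depend on d.

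| Unpenalised p | Z0 | Ratio if held to 0.025 | Ratio if held to 0.0475 |
|---|---|---|---|
| 0.001 | 3.291 | 1.27 | 1.02 |
| 0.0027 | 3.00 | 1.37 | 1.02 |
| 0.005 | 2.807 | 1.50 | 1.03 |
| 0.01 | 2.576 | 1.84 | 1.04 |
| 0.015 | 2.432 | 2.47 | 1.05 |
| 0.02 | 2.326 | 4.31 | 1.06 |

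The second row is the design case: 0.44 x sqrt(93/2) = 3.00, ratio (3.000 - 1.960)/(3.000 - 2.241) = 1.37. At 0.025 the ratio reaches 2 at Z0 = 2 x 2.241 - 1.960 = 2.52 (p = 0.0116), so two-fold or more needs p between 0.0116 and 0.025. At 0.0475 it needs p between 0.0451 and 0.0475.

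**Marginal example.** One dose wins, Z0 = 2.5, d = 0.20. Adjusted claim lost at (1 - 2.241/2.5)/0.20 = 52%. Raw 0.05 lost at (1 - 1.960/2.5)/0.20 = 108%, beyond the cap.

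**Averaged over the SAP's scenarios**, with truncated Hochberg re-applied to both doses at each common penalty:

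| | Scenario 1 | Scenario 2 |
|---|---|---|
| All rejected comparisons: median ratio | 1.10 | 1.20 |
| All rejected comparisons: ratio 2 or more | 3.7% | 8.8% |
| One dose wins: share of trials | 15.3% | 49.0% |
| One dose wins: median ratio | 1.47 | 1.33 |
| One dose wins: ratio 2 or more | 25% | 16% |
| Both win: median ratio, weaker / stronger dose | 1.02 / 1.16 | 1.04 / 1.18 |
| No tip by 100% at either criterion, d = 30% to 10% | 61% to 92% | 47% to 86% |
| Tips by 100% only at the adjusted criterion, d = 10% to 30% | 4% to 9% | 8% to 15% |

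**Check on the approximation.** A patient-level simulation with delta-adjusted multiple imputation (d about 20%, nine datasets significant at 0.025) gave ratios of 1.14 to 1.59. With Z0 = 2.707 and d = 0.194, for example, tipping came at 140% and 88%, against 142.5% and 88.8% from the formula. The standard-error increase ignored by the formula lowers tipping points slightly and hardly changes the ratio.

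**The case against.** The strongest reply is that the SAP never says the analysis stops at raw 0.05. It defines the tipping point by the overturning of the primary results, which are adjusted results, and it does not list this analysis among those exempt from Hochberg. A careful statistician could therefore read the adjusted criterion into 16.1.4.3. That stands as far as it goes: a reader might infer that the plan fixes the wrong threshold, and the documents do not support that. They leave the criterion open. But the defining phrase is not carried into the steps: the named outputs are unadjusted, no macro call appears, and the doses are searched separately.

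It can also be said that little is lost. Because 0.05 is the loosest level, every smaller penalty is run, and if both doses' pooled p-values are tabulated a reader can apply 0.025 and 0.0475 afterwards. That is fair, but the tipping delta actually reported would still be the wrong one.

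Finally, SAP 16.1.4 names two MNAR analyses, this one and placebo-based imputation, without ranking them, and no alpha is spent on either. Calling this the principal missing-data test would go beyond the text.

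**Conclusion.** The point holds as a gap between criterion and claim. Read with the 6.6 default, the tipping-point steps can report a penalty larger than the one that overturns the truncated-Hochberg result, and never a smaller one. The size is usually modest: a median of 10% to 20% over all rejected comparisons. The gap is wider when only one dose wins, and it grows as that dose's p-value approaches 0.025, which is where a tipping-point analysis is most needed.

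A reader might infer from the marginal example that robustness is often doubled. The SAP's own scenarios do not bear that out: two-fold or more occurs in about 4% to 9% of rejections, and in at most about a quarter of single-dose wins. The ratios rest on the SAP's design effects and a fixed standard error. The share reported as not tipping although the adjusted claim is lost (about 4% to 15%) also depends on the assumed 10% to 30% missing at Week 6. The primary test itself is unaffected.

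**What to change.** Add two sentences to SAP 16.1.4.3 and Appendix 3, Step 6. First, at each common delta the pooled p-values for both doses go through the same truncated Hochberg procedure (gamma = 0.9) as the primary analysis. Second, a dose's tipping point is the first delta at which its adjusted p-value exceeds 0.05. Both doses stay in the calculation after one has tipped, so that the survivor is held to 0.025. Tabulate raw and adjusted p-values side by side for every delta.

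The cost is one extra macro call per delta and slightly less favourable tipping points. No new data or imputations are needed, because Step 4 already applies a common percentage to both doses. If the adjusted reading was intended all along, the edit only records it.

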16.1.4.4. Impact of remote visits

To assess the impact of remote visits, primary MMRM analysis (see [Section 16.1.3](#)) will be repeated for MADRS Total Score after removal of all assessments conducted during remote visits.

16.1.4.5. Impact of COVID-19 Overall

To assess the potential impact of COVID-19 overall, primary MMRM analysis (see [Section 16.1.3](#)) will be repeated for MADRS Total Score by only keeping the records reported before 11 March 2020, corresponding to the WHO global pandemic declaration date.

16.1.5. SUPPORTIVE ANALYSIS OF PRIMARY EFFICACY VARIABLE(S)

16.1.5.1. Analysis of covariance

The primary efficacy endpoint will be analyzed using an ANCOVA on the ITT population as supportive analysis for each postdose visit. The model will include terms for treatment, region, and baseline MADRS total score as covariate. The LS mean of treatment differences (each SEP-4199 group minus placebo), their 2-sided 95% CIs, and the associated p-values will be obtained from the model.

Based on the ANCOVA, within group effect size is calculated as the absolute value of the LS Mean at

Document:

Author:

Version Number:

V2.0

Version Date:

21MAY2020

Template No: CS_TP_BS016 Revision 4
Effective Date: 01Apr2016

Reference: CS_WI_BS005

each visit divided by the standard deviation, obtained as the SE of the LS Mean multiplied by the square root of the treatment group change from baseline sample size at that visit. Between-group effect size at a visit will be calculated as the absolute value of the LS means difference from Placebo divided by the model estimate of the pooled standard error (the standard error of the LS mean difference divided by the square root of the sum of inverse treatment group change from baseline sample sizes).

16.1.5.2. Analysis on the per protocol population

The primary MMRM analysis will be repeated for the PP population to examine the impact of protocol deviations.

16.1.5.3. Analysis of dose-response

A supplementary analysis of the primary efficacy of SEP-4199 will be conducted on the ITT population to explore the dose response relationship using the generalized Multiple Comparison Procedure – Modeling (gMCP-Mod) methodology (Pinheiro 2014).

The gMCP-Mod approach to dose response will be implemented using R software, in particular the DoseFinding package ([APPENDIX 3](#)).

First, to obtain estimates of the dose response, an MMRM model on the ITT population with factors for treatment dose level, region, week, and baseline MADRS score as a continuous covariate will be used to model the change from baseline in MADRS score over time from the placebo and SEP-4199 groups. The LS mean of change from baseline in the MADRS total score at Week 6 for each SEP-4199 group and placebo and the corresponding variance-covariance matrix will be obtained from the model.

Next, the gMCP-Mod approach will use the estimates obtained from the MMRM model to analyze the dose response relationship at Week 6. The following set of candidate models for the dose response relationship will be considered ([APPENDIX 3](#)), but in case of inability to correctly fit data, a model could be removed from the analyses:

- Linear model (no parameters)
- Quadratic model (δ)
- E_{max} model (ED_{50})
- Sigmoidal E_{max} (ED_{50} , h)

Once a set of candidates are identified, the selection will be made using the MCPMod function from DoseFinding R package. The null hypothesis of a constant dose-response curve for the primary endpoint will be tested at the significance level of 5% against the one-sided alternative hypothesis of a non-constant dose response curve using the gMCP-Mod methodology.

For each of the dose-response models in the candidate set, the null hypothesis that the sum of the components of the optimal contrast vector is equal to zero will be tested. To do so, the contrast coefficients of each model are chosen so they maximize the power to detect the absence of dose response.

Under the null hypothesis, the vector of the optimal contrasts for the candidate models follows

Document:

Author:

Version Number:

V2.0

Version Date:

21MAY2020

Template No: CS_TP_BS016 Revision 4
Effective Date: 01Apr2016

Reference: CS_WI_BS005

asymptotically normal distribution. If the maximum asymptotic z statistic for the model contrast tests exceeds the critical value (corresponding to a unilateral test with alpha = 0.05), then the null hypothesis will be rejected and the proof of concept of a non null dose-response will be demonstrated.

The final detection of a significant dose-response signal is based on the adjusted p-value of the contrast test statistic. If no model contrast is significant (could be due to small sample size, high variance within the data, choice of candidate models, etc.), no dose response relationship will be further explored. Otherwise, the models with significant adjusted p-values will be selected for further investigation. The best/optimal model will be the one with the minimum Akaike Information Criterion (AIC) criterion. AIC for each model will be displayed in the table and the optimal model with the minimum AIC will be indicated.

The target dose of interest is the minimum effective dose (MED) level that will achieve a target effect of delta over placebo effect. The target dose of interest will be estimated using each significant model using inverse regression techniques. The target dose will be computed on both continuous and discrete scales using R software. Effective dose (ED_p), the dose level that achieves a certain percentage p of the maximum effect over placebo (ie, ED_{10} , ED_{25} , ED_{50} , ED_{75} , ED_{90}) will also be calculated on both continuous and discrete scales.

Alternatively, a weighted average of the significant model contrasts will also be used to calculate a weighted average of the estimated target dose.

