    VAR REGION MADRS_BASE MADRS_WK1 MADRS_WK2 MADRS_WK4 MADRS_WK6;
    CLASS TRTP REGION;
    MONOTONE REGRESSION(/ DETAILS);
    MNAR MODEL(MADRS_WK1 MADRS_WK2 MADRS_WK4 MADRS_WK6/ MODELOBS = (TRTP = 'Placebo'));
RUN;

```

The MODEL option specifies that only observations where TRT = "Placebo" are used to derive the imputation model for the missing postbaseline MADRS scores. Thus, the TRT variable is not specified in the VAR list. This approach is also known as jump to reference (jump to placebo in our case) where it is assumed that the discontinuations from the SEP-4199 treatment groups immediately change to have the distribution of the placebo group. This imputation model is also the imputation model that is used to impute missing postbaseline observations in the placebo group.

Step 3: Fit the primary MMRM model using each of the 1000 imputed datasets (BY _IMPUTATION_) and calculate the inferential statistics on each imputed dataset.

```

PROC MIXED DATA=zzz;
    BY _IMPUTATION_;
    CLASS SUBJID REGION TRTP WEEK;
    MODEL TOTCFB = MADRS_BASE REGION TRTP WEEK TRTP*WEEK / DDFM=KR;
    REPEATED WEEK/TYPE=UN SUBJECT=SUBJID;
    LSMEANS TRTP*WEEK /PDIFF CL;
    ODS OUTPUT DIFFS=CHGDIFF LSMEANS=CHGLSMN;
RUN;

```

Step 4. Use proc MIANALYZE to combine the estimates from Step 3 based on Rubin's imputation rules. See example for LS Means below.

```

PROC MIANALYZE DATA = CHGLSMN;
    BY TRTP WEEK;
    MODELEFFECTS ESTIMATE;

```

Document:

Author:

Version Number:

V2.0

Version Date:

21MAY2020

Template No: CS_TP_BS016 Revision 4
 Effective Date: 01Apr2016

Reference: CS_WI_BS005

```
STDERR STDERR;  
ODS OUTPUT PARAMETERESTIMATES = LSMN (DROP = PARM);  
RUN;
```

TIPPING POINT ANALYSIS

This analysis assumes that the data in the SEP-4199 treatment groups is not missing at random. The tipping point based assumption will be used, ie, the trajectories of the subjects in the SEP-4199 treatment groups after withdrawal are assumed to be worse by an amount of delta, after the MI using the MAR assumption.

The steps to implement this sensitivity analysis are as follows. For Japan cohort analysis, code must be adapted by removing REGION variable.

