The E_{\max} model is used to represent monotone, concave dose-response shapes. To distinguish it from the more general sigmoid E_{\max} model it is sometimes also called hyperbolic E_{\max} model. For the E_{\max} model, there is one parameter ED_{50} to be estimated.

- Sigmoidal E_{\max} : $f(d, \theta) = E_0 + E_{\max} d^h / (ED_{50}^h + d^h)$

The sigmoid E_{\max} model is an extension of the (hyperbolic) E_{\max} model by introducing an additional parameter h , that determines the steepness of the curve at the ED_{50} value. The sigmoid E_{\max} model describes monotonic, sigmoid dose-response relationships. For the Sigmoid E_{\max} model, there are two parameters ED_{50} and h to be estimated.

The next step is to determine the initial values of model parameters for the candidate models. Initial values for standardized model parameters can be calculated based on observed value at Week 6..

```
fitlinear<- fitMod(dose=dose, resp= resp, data = xxx, model="linear")
fitquadratic<- fitMod(dose=dose, resp= resp, data = xxx, model="quadratic")
fitemax<- fitMod(dose=dose, resp=resp, data = xxx, model="emax")
fitsigemax<- fitMod(dose=dose, resp=resp, data = xxx, model="sigEmax")
```

Note: Dose is 0 for placebo, 200 for SEP-4199 200mg/day and 400 for SEP-4199 400mg/day. Resp is the response so change from baseline at Week 6 in MADRS Total Score.

Document:

Author:

Version Number:

V2.0

Version Date:

21MAY2020

Template No: CS_TP_BS016 Revision 4
Effective Date: 01Apr2016

Reference: CS_WI_BS005

Based on an estimate of the dose-response vector and its associate variance/covariance matrix, optimal contrast will be computed for each model to maximize the power to test the null hypothesis of a constant dose-response curve. To obtain this estimate, an MMRM model with factors for treatment dose level, region, week, and baseline MADRS score as a continuous covariate will be used to model the change from baseline in MADRS score over time from the placebo and SEP-4199 groups for the ITT population. This analysis can be performed using the SAS software ([Dmitrienko, 2017](#)).

```

PROC MIXED;
  CLASS SUBJID REGION TRTPN WEEK;
  MODEL TOTCFB = TOTBL REGION TRTPN WEEK TRTP*WEEK / DDFM=KR RESIDUAL;
  REPEATED WEEK/TYPE=UN SUBJECT=SUBJID;
  LSMEANS TRTPN*WEEK /PDIFF CL COV;
  *ODS OUTPUT LSMEANS=MUH (KEEP=TRTPN WEEK ESTIMATE);
  *ODS OUTPUT LSMEANS=COVH (KEEP=TRTPN WEEK COVx COVy COVz) ;
RUN;

```

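### The MMRM that feeds the gMCP-Mod dose-response analysis is worded without a treatment-by-week term, and its code names the term inconsistently, so as written it does not supply Week 6 dose effects

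*SAP*

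**What the plan says.** SAP Section 16.1.5.3 obtains the dose-response estimates from "an MMRM model on the ITT population with factors for treatment dose level, region, week, and baseline MADRS score as a continuous covariate". The Appendix 3 text on MCP-Mod repeats the list: "an MMRM model with factors for treatment dose level, region, week, and baseline MADRS score as a continuous covariate". Neither includes treatment-by-week. Section 16.1.3, by contrast, defines the primary MMRM "with factors for treatment group, week, region, baseline MADRS total score, and the treatment-by-week interaction".

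The output that Section 16.1.5.3 wants from the model is specific to one visit: "The LS mean of change from baseline in the MADRS total score at Week 6 for each SEP-4199 group and placebo", together with the covariance matrix.

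The Appendix 3 code for this step has three relevant statements:

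- CLASS: "CLASS SUBJID REGION TRTPN WEEK"
- MODEL: "MODEL TOTCFB = TOTBL REGION TRTPN WEEK TRTP*WEEK / DDFM=KR RESIDUAL"
- LSMEANS: "LSMEANS TRTPN*WEEK /PDIFF CL COV"

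The primary MMRM code at the start of Appendix 3 uses TRTPN*WEEK in both MODEL and LSMEANS. The protocol's MCP-Mod paragraph (Section 15.3.5.1.2) names no input model, so the SAP is the only specification.

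**The concern.** An MMRM with dose and week as main effects only has one parameter per dose, shared by Weeks 1, 2, 4 and 6. A Week 6 mean can still be computed from it, but the difference between a dose and placebo at Week 6 is a weighted average over all visits. For an effect that builds up over six weeks, that average falls short of the Week 6 effect.

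The code does not settle which model applies. It contains an interaction, but in a variable that the CLASS statement does not list, and it asks for least-squares means of a different effect.

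At stake are the dose means (muH) and their covariance (covH). They drive the contrast test statistics, the model fits in the Mod step, the gAIC selection and the target-dose estimates.

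**Working it through.** **Inputs.** From SAP Section 3.4: Week 6 difference 3.85 (absolute size), SD 8.745, 93 per arm. From Appendix 3: visits at Weeks 1, 2, 4 and 6. The documents do not give the time course of the effect, the SDs at earlier visits or the correlations, so these are assumed.

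**Check of the inputs.** 3.85 / 8.745 = 0.440, the stated effect size. Simulating the truncated Hochberg test (γ = 0.9, one-sided 0.025, 93 per arm) gives 0.906 for at least one rejection and 0.753 for both. SAP Table 8 has 0.9027 and 0.7517. This confirms the inputs; the point does not depend on the power figure.

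**What the worded model estimates.** With complete data, let d be the vector of true differences at the four visits and S the within-subject covariance. The generalised-least-squares dose effect is

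(1′S⁻¹d) / (1′S⁻¹1) = Σ wₖdₖ, with Σ wₖ = 1.

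It takes the same value at every visit. If every dₖ is 3.85, it is 3.85 whatever the weights.

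**Illustration.** Two assumed build-ups at Weeks 1/2/4/6: slow, 0.8/1.6/2.9/3.85; fast, 1.5/2.5/3.4/3.85. Two SD patterns: constant 8.745, and growing 5/6.3/7.8/8.745. Two correlations: exchangeable 0.6, and exponential decay of 0.75 per two weeks.

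| SD | Correlation | Weights, Weeks 1/2/4/6 | Slow | Fast |
|---|---|---|---|---|
| Constant | Exchangeable | 0.25/0.25/0.25/0.25 | 2.29 | 2.81 |
| Constant | Exponential | 0.39/0.08/0.11/0.42 | 2.37 | 2.77 |
| Growing | Exchangeable | 0.83/0.28/0.00/−0.10 | 0.72 | 1.54 |
| Growing | Exponential | 1.20/−0.28/−0.03/0.11 | 0.86 | 1.43 |

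First row, slow: (0.8 + 1.6 + 2.9 + 3.85) / 4 = 9.15 / 4 = 2.29, or 59% of 3.85. Across the table the estimate is 59–73% of the Week 6 effect with constant SD and 19–40% with growing SD. A second set of assumptions (linear, early-plateau and late effects; SDs constant or 5/6.5/8/8.745) gives 1.54 to 3.13 and −0.27 to 1.96 respectively.

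**Effect on ED_p.** Suppose the 200 mg effect is c times the 400 mg effect at every visit. Then Σ wₖ(c·dₖ) = c·Σ wₖdₖ, so the ratio of the two doses is kept and ED_p, a percentage of the maximum effect, does not move. If the time courses differ, it can move. In a 500-run simulation with an early plateau for 200 mg, linear growth for 400 mg and growing SD, the true Week 6 effects were −1.93 and −3.85. The additive model averaged −0.98 and −0.48; the model with the interaction averaged −1.97 and −3.90.

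**The code, by reading (not run).** TRTP appears in MODEL but not in CLASS. Elsewhere in Appendix 3 it holds text; the placebo-based imputation step selects on it ("MODELOBS = (TRTP = 'Placebo", closing characters cut). LSMEANS names TRTPN*WEEK, which is not an effect in that MODEL statement. PROC MIXED should reject both, so muH and covH would not be produced.

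**The case against.** The strongest reply is that the intended model is plain. The code contains a treatment-by-week term, LSMEANS asks for treatment-by-week means, the note after the code takes the covariance columns at Week 6, and the same model is printed correctly for the primary analysis. TRTP*WEEK reads as a one-letter slip. The printed code would also fail visibly, and deleting the interaction to match the text would fail too, because LSMEANS needs it. To obtain the attenuated estimates, a programmer would have to drop the term and also replace the LSMEANS statement. This stands, and it makes the harmful outcome unlikely. It does not remove the conflict: the text defines a different model twice, and a programmer repairing the code could take the text as authority.

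Four stronger readings are tempting, and the documents do not support them:

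- **The MMRM output is the only input.** Candidate-shape starting values come separately from observed Week 6 data and enter the contrast coefficients.
- **Early visits always dominate.** With constant SD and exponential decay, Week 6 has the largest weight (0.42).
- **The ED estimates are necessarily wrong, or the dose order reverses.** Both need different time courses by dose; the reversal is one constructed scenario.
- **The target dose becomes unreachable because the illustrative values lie below the coded Delta of 3.5.** Later calls in the appendix leave Delta open, to be explored from the results.

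The shortfall in the point estimate also overstates the loss in the test, because averaging reduces the standard error. With constant SD and complete data, the table's cases give z of about 2.1 to 2.6, against 3.85 / (8.745 × √(2/93)) = 3.0 for the Week 6 contrast.

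**Conclusion.** Wrong as written, and minor. The worded input model does not estimate Week 6 dose effects unless the effect is constant from Week 1, and the printed code would not deliver the required means and covariance. This follows from the model terms alone. The size does not: 2.3–2.8 points with constant SD, or 0.7–1.5 with growing SD, in place of 3.85, holds only under the assumed build-ups and correlations.

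A reader might infer that the sponsor chose an additive analysis or that the efficacy conclusions are in doubt. Neither follows. The interaction was almost certainly intended, the analysis is supplementary, and the primary MMRM, the gatekeeping procedure and the sample size are untouched.

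**What to change.** - In SAP Section 16.1.5.3 and the matching Appendix 3 text, state that the gMCP-Mod input model is the Section 16.1.3 MMRM, including treatment-by-week.
- In the Appendix 3 MCP-Mod code, change TRTP*WEEK to TRTPN*WEEK in the MODEL statement.
- State that muH and covH are taken from the Week 6 rows of LSMEANS TRTPN*WEEK.

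The cost is two sentences of text, one variable name and a clarifying line. No new data are needed, and no other analysis changes.
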